## **5.2.2 Treatment Period**

### **5.2.2.1 Cycle 1, Day 1: First Infusion**

The following evaluations will be performed on Day 1 of Cycle 1:

- 1) Perform directed physical examination (if applicable, record new findings as AEs or SAEs)
- 2) Assess for AEs and SAEs since screening visit
- 3) Update concomitant medications
- 4) Obtain vital signs (temperature, blood pressure, pulse, respiratory rate) including weight prior to infusion (-1 day allowed for weight)
- 5) Assess ECOG performance status
- 6) Collect blood for baseline samples prior to infusion:
  - Serum chemistry (-1 day allowed)
  - Hematology (-1 day allowed)
  - Coagulation parameters (-1 day allowed)
  - Anti-MEDI-575 antibodies
  - MEDI-575 serum concentration
  - Circulating soluble proteins
  - Circulating apoptotic markers
- 7) Collect urine for routine urinalysis and urine pregnancy test; ensure result is negative (-1 day allowed)
- 8) Perform 12-lead ECG prior to infusion and post infusion (+ 5 minutes)
- 9) Administer PRO questionnaires (-3 days allowed)
  - EORTC QLQ-C30
  - EORTC QLQ-BN20

- 10) Administer MEDI-575 infusion
- 11) Obtain vital signs at the end of the infusion ( $\pm$  5 minutes) and 30 minutes post-completion of infusion ( $\pm$  5 minutes)
- 12) Obtain blood for PK analysis:
  - MEDI-575 serum concentration: immediately post-completion of infusion ( $\pm$  5 minutes)

#### **5.2.2.2 Cycle 1, Day 8**

The following evaluations will be performed on Day 8 of Cycle 1:

- 1) Collect blood samples for:
  - Serum chemistry
  - Hematology
  - MEDI-575 serum concentration
  - Circulating soluble proteins
  - Circulating mRNA/miRNA
- 2) Collect urine for routine urinalysis
- 3) Assess for AEs and SAEs
- 4) Update concomitant medications

#### **5.2.2.3 Cycle 1, Day 15**

The following evaluations will be performed on Day 15 of Cycle 1:

- 1) Collect blood samples for:
  - Serum chemistry
  - Hematology
  - MEDI-575 serum concentration
  - Circulating soluble proteins
  - Circulating apoptotic markers
- 2) Collect urine for routine urinalysis
- 3) Assess for AEs and SAEs
- 4) Update concomitant medications

### **5.2.3 Cycle 2 and Beyond, Day 1 (+7 Days)**

The following evaluations will be performed on Day 1 of Cycle 2 and all subsequent cycles:

- 1) Perform directed physical examination (if applicable, record new findings as AEs or SAEs)
- 2) Assess for AEs and SAEs
- 3) Update concomitant medications
- 4) Obtain vital signs (temperature, blood pressure, pulse, respiratory rate) including weight prior to infusion (-1 day allowed for weight)
- 5) Assess ECOG performance status
- 6) Collect blood for baseline samples prior to infusion:
  - Serum chemistry (-1 day allowed)
  - Hematology (-1 day allowed)
  - Coagulation parameters (-1 day allowed)
  - Anti-MEDI-575 antibodies
  - MEDI-575 serum concentration
  - Circulating soluble proteins
  - Circulating apoptotic markers
- 7) Collect urine for routine urinalysis and urine pregnancy test (women of childbearing potential only. (-1 day allowed)
- 8) Perform 12-lead ECG prior to infusion
- 9) Administer PRO questionnaires (-3 days allowed)
  - EORTC QLQ-C30
  - EORTC QLQ-BN20
- 10) Administer MEDI-575 infusion
- 11) Obtain blood for PK analysis:
  - MEDI-575 serum concentrations: Immediately after ( $\pm$  5 minutes) completion of infusion
- 12) Assess for AEs/SAEs observed during treatment

### **5.2.4 Every 2 Cycles, Beginning with Cycle 3**

The following evaluations will be performed every 2 cycles (ie, every 6 weeks) unless otherwise indicated, beginning at Cycle 3 (eg, Cycle 3, Cycle 5, etc.)

- 1) Assess for disease response:
  - MRI scan (within 7 days prior to start of cycle)

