#### **4.5.2 Treatment Regimens**

Subjects will be treated with MEDI-575 at 25 mg/kg on Day 1 every 21 days until documentation of disease progression, initiation of alternative anticancer therapy, unacceptable toxicity, or another reason for treatment discontinuation (see Section 4.2.3) is observed. In Cycle 2 and beyond, a dose can be delayed up to 7 days for unavoidable scheduling issues. MEDI-575 may be withheld for up to 21 days until resolution to  $\leq$  Grade 1 toxicity after agreement with the sponsor. Subjects who demonstrate stable disease or better may continue to receive MEDI-575 under the criteria above. Each new cycle will begin no fewer than 21 days after the last dose of the previous cycle.

Subjects who receive any number of doses of MEDI-575 and proceed to surgical resection as subsequent therapy for GBM may be asked to allow procurement of resected tissue to determine intratumoral levels of MEDI-575.

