**Table 5.2-2 Schedule of Study Procedures: Follow-up Period**

Procedure	Follow-up/Post Therapy	
	30-Days After Last Dose (+ 3 days) 60-Days After Last Dose (± 5 days) 90-Days After Last Dose (± 5 days)	Every 3-Months After Last Dose (±2 weeks)
Physical examination	X	X (focused physical exam)
12-lead ECG	X (30-day post visit only)	
Vital signs, including weight	X	
Hematology	X	
Serum chemistry	X	
Routine urinalysis	X	
Urine pregnancy test	X (90-day post visit only)	
AE/SAE assessment	X	
Concomitant medications	X (30-day post visit only)	
MRI scan		X
ECOG Performance Status	X	X
Subsequent anticancer therapy	X	X
Survival status	X	X
MEDI-575 serum concentration	X	
Anti-MEDI-575 antibodies	X	X (first 3-month visit only)
Circulating soluble proteins	X	
Circulating apoptotic markers	X	

AE = adverse event; ECG = electrocardiogram, ECOG = Eastern Cooperative Oncology Group; MRI = magnetic resonance imaging; SAE = serious adverse event

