### **5.2.6.3 Every 3 Months (Plus or Minus 14 Days) After Last Treatment**

The following evaluations will be performed every 3 months ( $\pm$  14 days) after the last treatment as specified (for subjects who discontinue treatment due to reasons other than disease progression or initiation of alternative anticancer therapy, these evaluations will be performed until documentation of disease progression, initiation of alternative anticancer therapy, or the end of study [defined as 9 months post the date the last subject is entered on the trial or when sponsor stops the study]):

- 1) Evaluation of disease
  - MRI scan
  - Focused physical examination
  - ECOG performance status

- 2) Blood collection for anti-MEDI-575 antibodies (3-month post visit only)
- 3) Survival status and subsequent anticancer therapy must be collected in every subject regardless of the reason for treatment discontinuation. Assessment can be either performed on a clinic visit or telephone contact until death or the end of the study

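### MRI timing follows dosing cycles rather than the calendar, so no scan is tied to the 6-month landmark and some earlier progressions are counted as progression-free in PFS-6

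*Protocol*

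**What the plan says.** Section 5.2.4 ties tumor assessment to the cycle count: "The following evaluations will be performed every 2 cycles (ie, every 6 weeks) unless otherwise indicated, beginning at Cycle 3". The window is also relative to the cycle: "MRI scan (within 7 days prior to start of cycle".

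Section 4.5.2 lets cycles lengthen but not shorten. It sets a floor, "Each new cycle will begin no fewer than 21 days after the last dose of the previous cycle", and allows two kinds of slippage: "a dose can be delayed up to 7 days for unavoidable scheduling issues" and, for toxicity, "MEDI-575 may be withheld for up to 21 days until resolution to" Grade 1 or lower.

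Off treatment, Table 5.2-2 places MRI under "Every 3-Months After Last Dose (±2 weeks". Section 5.2.6.3 applies that interval "for subjects who discontinue treatment due to reasons other than disease progression or initiation of alternative anticancer therapy, these evaluations will be performed until" progression, new therapy or end of study. An MRI is also due at treatment discontinuation (Section 5.2.5).

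PFS runs from first dose to documented progression or death (Section 7.3.2.1). The primary analysis is the Kaplan-Meier PFS-6 rate with a 2-sided 90% CI (Section 7.3.1). The study is positive if the lower bound is at least 16% (Section 7.5). The protocol does not express 6 months in days or weeks.

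**The concern.** The primary endpoint is a survival probability at one time point, but the assessments that reveal most events are not anchored to it. Section 5.2.4 treats two cycles and six weeks as the same interval. Section 4.5.2 means they separate after any late dose, and the delays accumulate because a cycle can never be shorter than 21 days.

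Progression is dated when documented, so a progression arising between the last pre-landmark scan and the landmark, and not picked up clinically, enters the Kaplan-Meier curve after 6 months. The estimate then reflects PFS at the last scan before 6 months, a time that varies with dose delays and discontinuation. This is a single-arm trial with one decision threshold, so no control arm shares the distortion. A SAP can define the landmark and handle windows, but it cannot supply a scan that the protocol never scheduled.

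**Working it through.** **The plan's own figure.** Inputs from Section 7.5: n = 50, null 16%, alternative 30%, 2-sided alpha 0.1. A one-sample normal test with the null variance at the critical value gives

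power = Φ[(0.30 − 0.16 − 1.645·√(0.16·0.84/50)) / √(0.30·0.70/50)] = Φ(0.844) = 80.1%,

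which matches the stated 80%. The critical value is 0.16 + 0.085 = 0.245, so success needs about 13 of 50. The exact binomial for at least 13 of 50 gives 4.8% at a true 16% and 77.7% at a true 30%. This rule stands in for the Kaplan-Meier lower bound below.

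**Scan days with no delay** (days elapsed since first dose; window is the 7 days before the cycle):

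| Scan | Cycle start | Scan window |
|---|---|---|
| Cycle 7 | 6 × 21 = 126 | 119–126 |
| Cycle 9 | 8 × 21 = 168 | 161–168 |
| Cycle 11 | 10 × 21 = 210 | 203–210 |

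Taking 6 months as 182.6 days (assumption), the last scan before it is about 15 to 22 days early. The next is about 20 to 27 days late.

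**Effect of delay.** With cumulative delay D by Cycle 9, the scan window is 161 + D to 168 + D. The scan can miss the landmark once D exceeds 14 days (168 + 15 = 183) and always does once D exceeds 21 days (161 + 22 = 183). Eight intervals at up to 7 days each allow 56 days. A single full 21-day hold moves the window to 182–189. Cycle 7 is then the last scan before the landmark.

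**Off treatment.** If the last dose is Cycle 3 (day 42), 3-monthly scans (91 days) fall near days 133 and 224, each ±14 days. If it is Cycle 6 (day 105), the next falls at 196 ± 14, or days 182–210. Neither pattern secures a scan just before the landmark.

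**Size.** Assume exponential PFS and a true PFS-6 of 16%. If progression is found only by scan, the apparent rate is 0.16^(d/182.6), where d is the day of the last scan before 6 months. If half of the gap progressions are caught clinically when they occur, the apparent rate is the average of that value and 16%. False-positive rates are P(at least 13 of 50).

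| Situation | d | Scan only: apparent / false positive | Half caught clinically |
|---|---|---|---|
| Landmark scan at 6 months | 182.6 | 16.0% / 4.8% | 16.0% / 4.8% |
| No delay | 168 | 18.5% / 12% | 17.3% / 8% |
| No delay | 161 | 19.9% / 18% | 17.9% / 10% |
| Cycle 9 scan late, for all subjects | 140 | 24.5% / 46% | 20.3% / 20% |

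The last row takes a Cycle 7 scan moved to about day 140 by delay spread over the cycles. It is a bound for the affected subjects, not a forecast for the trial.

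**If 6 months means 24 weeks (168 days).** The undelayed Cycle 9 scan falls on or up to 7 days before the landmark. The apparent rate is between 16.0% and 0.16^(161/168) = 17.3%, with false positives of 4.8–7.9%. A delay of more than 7 days puts the whole window past day 168.

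**The case against.** The strongest reply is that the bias is smaller than a scan-only calculation suggests, and much of it stands. Death and clear clinical deterioration count at their own dates (Section 7.3.2.1, Appendix 4). Physical examination and ECOG status are recorded every cycle, extra tumor assessments are allowed at the investigator's discretion (Section 5.3.7), and there is a discontinuation MRI. Subjects who start new therapy or drop out without progression are censored at their last assessment. A reader might infer that progressions before 6 months are generally counted as successes. The documents do not support that: only those arising after the last pre-landmark scan and not found clinically are affected.

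A reader might also infer false-positive rates of 40–51%. Those need an average 3-day slip on every cycle for every subject with scan-only detection (last scan at days 137–144). Nothing in the protocol supports that rate; delays are limited to unavoidable scheduling problems and toxicity holds agreed with the sponsor, and Phase 1 reported no DLTs. Early stopping without progression or new therapy should likewise be uncommon, because treatment otherwise continues to progression.

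Finally, the 16% benchmark comes from another single-arm trial (Section 7.5) whose scan schedule is not given. If it carries a similar scan-interval effect, part or all of the bias cancels. This limits any claim about the comparison with 16%. It does not remove the dependence of this trial's own estimate on dose delays.

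**Conclusion.** The point holds in mechanism and is moderate in size. The schedule ties no MRI to 6 months, the equation of two cycles with six weeks fails once a dose slips, and undetected progressions in the resulting gap can only raise the estimate relative to the trial's own true PFS-6.

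With no delays, exponential PFS and a 182.6-day landmark, a true 16% reads as about 17–20%. The one-sided false-positive rate is about 8–18% instead of 5%, depending on how much progression is caught clinically. For subjects whose cumulative delay exceeds about 14–21 days by Cycle 9 the bias is larger: about 20–25% apparent if it applied to everyone. With a 24-week landmark the no-delay bias nearly disappears, but delays beyond about 7 days bring it back. The delay frequency and the share of progression detected clinically are not in the documents. That the trial is biased upward against the 16% benchmark is a tempting reading that cannot be established from them.

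**What to change.** Schedule MRI by calendar weeks from Cycle 1 Day 1, every 6 weeks, independent of dose delays or holds, and state the PFS-6 landmark in days. Align the landmark scan with the analysis. Either place its window wholly on or before the landmark day, or evaluate the Kaplan-Meier estimate at the end of that window, so that a progression found at the landmark scan counts as an event by 6 months. Keep the same MRI calendar up to the landmark for subjects who stop treatment without progression.

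The alignment matters. Replacing the Cycle 9 scan with one at week 26 ±7 days (days 175–189), while still reading the curve at 182.6 days, would date progressions found on days 183–189 after the landmark. For those subjects the last informative scan would be week 18 (day 126), where a true 16% reads as 0.16^(126/182.6) = 28% under scan-only detection. That is worse than the present on-schedule figure.

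The cost is an amendment to Section 5.2.4, Section 5.2.6.3 and Tables 5.2-1 and 5.2-2, scans that sometimes do not coincide with dosing visits, and one or two additional MRIs for the few subjects who stop early without progression. Dosing rules are unaffected.

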### **5.2.5 Treatment Discontinuation Visit**

The following evaluations will be performed at the time (or up to 5 days after) the subject completes therapy or is withdrawn/discontinued from the study therapy, or at the time of first objective disease progression, whichever comes first. Any procedures conducted within 14 days before treatment discontinuation (eg, procedures conducted on Day 1 of a cycle) do not need to be repeated at the treatment discontinuation visit.

- 1) Perform complete physical examination (if applicable, record new findings as AEs or SAEs)
- 2) Assess for AEs and SAEs
- 3) Update concomitant medications
- 4) Obtain vital signs (temperature, blood pressure, pulse, respiratory rate) including weight (-1 day allowed for weight)
- 5) Assess ECOG performance status
- 6) Collect blood samples for:
  - Serum chemistry (-1 day allowed)
  - Hematology (-1 day allowed)
  - Coagulation parameters (-1 day allowed)
  - Anti-MEDI-575 antibodies
  - MEDI-575 serum concentration
  - Circulating soluble proteins
  - Circulating apoptotic markers
  - Circulating mRNA/miRNA
- 7) Collect urine for routine urinalysis (-1 day allowed)
- 8) Perform 12-lead ECG

- 9) Obtain consent and collect fresh tissue tumor biopsy (optional)
- 10) Administer PRO questionnaires (-3 days allowed)
  - EORTC QLQ-C30
  - EORTC QLQ-BN20
- 11) Disease evaluations:
  - MRI scan

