### **7.3.2.2 Secondary Endpoints of Safety and Tolerability of MEDI-575**

Secondary safety endpoints of this study include:

- Adverse events and SAEs occurring from the signing of an ICF to 90 days after the last dose or until the subject begins another anticancer therapy, whichever occurs first.

- Changes in clinical laboratory and ECG evaluations from baseline.

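### From Cycle 2 on, the 14-day waiver at the Treatment Discontinuation visit lets pre-infusion Day 1 labs and ECG replace the only scheduled safety sample between the last dose and the 30-day visit

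*Protocol*

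**What the plan says.** Section 5.2.5 places the Treatment Discontinuation visit "at the time (or up to 5 days after) the subject completes therapy or is withdrawn/discontinued from the study therapy", or at first objective progression if that comes sooner. The visit includes chemistry, hematology, coagulation, urinalysis and a 12-lead ECG. It carries a waiver: "Any procedures conducted within 14 days before treatment discontinuation (eg, procedures conducted on Day 1 of a cycle) do not need to be repeated". The waiver does not require the earlier procedure to follow the last infusion, or to follow the event that led to stopping.

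For Day 1 of Cycle 2 and later, Section 5.2.3 says "Collect blood for baseline samples prior to infusion" (chemistry, hematology and coagulation among them) and "Perform 12-lead ECG prior to infusion". Urinalysis is listed ahead of the infusion as well. Day 8 and Day 15 visits exist in Cycle 1 only (Sections 5.2.2.2 and 5.2.2.3, Table 5.2-1).

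The next fixed visit is 30 days (+3) after the last treatment (Section 5.2.6.1). It repeats chemistry, hematology, urinalysis and ECG. Coagulation appears neither there nor anywhere else in Table 5.2-2.

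Section 7.3.2.2 names as a secondary safety endpoint: "Changes in clinical laboratory and ECG evaluations from baseline".

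**The concern.** The discontinuation visit is the only scheduled occasion after a Cycle 2 or later infusion, and before the 30-day visit, on which safety labs and an ECG are taken. The waiver makes those tests optional, and its own example points to Day 1 procedures. If the subject was infused on that Day 1, the procedures relied on were done before the dose, and so before any toxicity it caused.

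The subjects concerned are not a random subset: they are those who stop soon after a dose, including those who stop because of an adverse event. For them the plan may hold no scheduled laboratory or ECG value close to the event, although change in these measures is a declared endpoint. Coagulation is hit hardest, because no later visit collects it. The only Phase 1 serious event assessed as possibly related was a pulmonary embolism (Section 1.2.3), although Section 1.4 notes that the subject had a prior history of one.

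**Working it through.** The protocol states no figure for this gap, so there is none to reproduce. The check is a reading of the visit schedule plus calendar arithmetic.

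**Inputs**
- Waiver window: 14 days before treatment discontinuation (Section 5.2.5).
- Visit window if not waived: 0 to 5 days after discontinuation (Section 5.2.5).
- Dosing: one infusion on Day 1 of a 21-day cycle (Section 4.5.2).
- Cycle 2+ Day 1 labs and ECG: before the infusion, with a further 1-day allowance for labs (Section 5.2.3).
- Next fixed labs and ECG: 30 to 33 days after the last dose (Section 5.2.6.1), which is Day 31 to Day 34 counting the dose day as Day 1.

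**Which stops are covered**
- Day 1 + 14 days = Day 15. Procedures done on Day 1 cover a stop on any day up to Day 15.
- If labs were drawn the day before Day 1, cover for labs ends on Day 14.

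**Gap from stopping to the next scheduled labs and ECG if the waiver is used (Cycle 2+)**
- Stop on Day 2: 31 − 2 = 29 days to 34 − 2 = 32 days.
- Stop on Day 10: 31 − 10 = 21 days to 34 − 10 = 24 days.
- Stop on Day 15: 31 − 15 = 16 days to 34 − 15 = 19 days.
- Without the waiver: 0 to 5 days in every case.

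**Tests with no later scheduled value**
- Chemistry, hematology, urinalysis: repeated at 30, 60 and 90 days (Sections 5.2.6.1 and 5.2.6.2).
- ECG: repeated at 30 days only.
- Coagulation: not repeated, so a waived sample leaves no scheduled value after the last dose.

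**Where the gap is smaller or absent**
- Cycle 1 has an ECG shortly after the infusion, and chemistry, hematology and urinalysis on Days 8 and 15.
- A stop after more than 21 days of withholding (Table 4.5.4.3-1) lies outside 14 days from the Day 1 infusion. The relevant route is an immediate stop, such as an adverse event judged to contraindicate further dosing (Section 4.2.3).
- If the subject attends Day 1, has labs and ECG, and stops without being infused, those values come about 21 days after the last dose and serve properly as discontinuation values.

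**The case against.** The strongest reply is that little safety information is at risk. The waiver is permissive, so a site may still repeat everything. A subject stopped for a laboratory toxicity must already have an abnormal post-dose result, and Section 5.3.2 asks for clinically significant abnormal tests to be repeated, preferably within 24 to 48 hours. Section 6.1.1 makes laboratory and ECG findings that need action reportable as adverse events. Section 6.4.1 collects adverse events to 90 days after the last dose or the start of another anticancer therapy, and follows them to resolution. The Day 1 example is also sensible where progression is found around Day 1 and no infusion is given.

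Most of this stands, and it limits the point. It does not close the gap for a subject stopped for a symptomatic event with no abnormal laboratory result in hand, nor for the ECG or coagulation. Repeat testing starts only once an abnormal value has been seen.

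A reader might infer more than the protocol supports:
- *That pre-dose values will be analysed as discontinuation values, so toxicity is understated.* The protocol does not say how a waived visit is handled in analysis, and Section 7.1 leaves analysis detail to the SAP, which is not shown.
- *That the waived MRI harms the progression endpoint.* Appendix 4 already counts clear clinical deterioration due to the tumor as progression, Section 5.3.7 allows additional tumor assessments, and Section 5.2.6.3 continues MRI for subjects who stop for reasons other than progression or new therapy.
- *That PK all precedes the last dose.* Section 5.2.3 also schedules "MEDI-575 serum concentrations: Immediately after" the infusion.
- *That two thirds of stops (14 of 21 days), or every stop in the window, is affected.* This is a share of calendar days, not of discontinuations, and use of the waiver is optional.

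**Conclusion.** The point holds for laboratory tests and ECG, from Cycle 2 on, in subjects who were infused on Day 1 and stopped for an adverse event up to about Day 15. If the site uses the waiver, the first scheduled post-dose labs and ECG fall 30 to 33 days after the dose, and no coagulation value after the last dose is scheduled. The consequence is weaker data for one secondary safety endpoint. It is not a missed event and does not affect the primary PFS-6 analysis.

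The conclusion assumes that sites apply Section 5.2.5 as written and that no unscheduled tests are done. The number affected cannot be worked out, because no discontinuation rate is given. It is probably small: Section 1.2.3 reports no dose-limiting toxicities and mostly Grade 1 or 2 events in Phase 1. This is an inexpensive improvement, not a flaw that threatens the trial.

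**What to change.** Reword the waiver in Section 5.2.5 along these lines:

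*Procedures done in the 14 days before treatment discontinuation and after the last infusion need not be repeated; laboratory tests and ECG are repeated when treatment stops because of an adverse event, unless already done after onset of that event.*

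The Day 1 example may stay if it is limited to a Day 1 visit at which no infusion was given. If the sponsor does not want the last-infusion condition to reach the other procedures at this visit, such as MRI, it can be confined to laboratory tests and ECG; the point made here needs no more.

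The cost is one sentence and, for a minority of subjects, labs and an ECG that are done instead of waived. The visit and these tests are already in the schedule, and no dosing or stopping rule changes.
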